#### 2.5 Quality control

The SAP is consistent with the underlying study protocol. If there is a need for deviating substantially from the protocol-defined analysis, this is described in detail. The methods described in this SAP are mandatory for statistical programming.

Quality control (QC) of statistical programming will be performed according to the QC plan, which specifies all planned actions to ensure that the performed analyses are correct, traceable and in line with the planned analysis as specified in the SAP. The QC plan also includes filing of statistical programs, outputs and documentation of QC. It is finalized by the project statistical programmer before the start of any programming activities.

Documentation of QC is filed in the trial master file.

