## 3.2 Secondary objectives

The secondary objectives of this study are:

- To describe PD medication management, and the main reasons justifying their use, directly prior to LCIG initiation, at LCIG initiation and during long-term LCIG treatment
- To describe LCIG infusion settings and substantial dose adjustments and the respective reasons
- To describe the Healthcare Resource Utilization (HCRU)
- To identify the physician's and patient's/caregiver's overall preference for the pharmacological treatment approach using LCIG as monotherapy vs. LCIG plus add-on PD medication
- To identify predictors for achieving long-term monotherapy with LCIG vs. LCIG plus add-on PD medication, based on the patient's profile and the physician's profile
- To describe the latency from LCIG initiation until LCIG is given as a monotherapy and the average duration of LCIG monotherapy
- To describe the latency from the initiation of LCIG therapy until the introduction or tapering of each PD medication, or until substantial dose adjustments of LCIG
- To evaluate the percentage of patients who are on LCIG monotherapy, PD medication management and HCRU for the participating countries who have enrolled a minimum of 20 study subjects

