#### 4.2 Study population

Approximately 400 patients were to be included in the study. The study population consists of adult patients diagnosed with APD, on current treatment with LCIG, and treated with LCIG for at least 12 months prior to study inclusion.

The participating sites were to be hospitals or clinics experienced in treating patients with APD, and with experience in LCIG treatment. Participating physicians should have been involved in the respective patient's management since initiation of LCIG therapy. All eligible patients at a given site were to be enrolled consecutively in order to minimize selection bias.

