#### 4.2.1 Inclusion criteria

Patients were eligible for study participation if all of the following criteria were fulfilled:

- 1. Patients diagnosed with APD and on LCIG treatment for at least 12 months
- 2. Patient must have been on continuous LCIG treatment for at least 80% of days in the preceding year
- 3. Patients must be treated by the same physician (PI or co-investigator) since the initiation of LCIG treatment
- 4. Decision to treat with LCIG was made and therapy was started by the physician prior to any decision to approach the patient to participate in this study
- 5. Prior to any data collection, the patient, or legal authorized representative (LAR) has voluntarily signed an Authorization for Use/Disclosure of Data (AUDD)/informed consent form (ICF) according to national regulations after the study has been explained and the subject has had the opportunity to have questions answered

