- Number of pills in addition to LCIG the patient would be willing to take each day
- Problems before starting LCIG (multiple answers)
- Help required to remember to take the medication (yes, no)
- Influence on the patient's decision to start treatment with LCIG (yes, no, missing)
  - If not 'no':
    - Doctor
    - Caregiver
    - Other family member
- Any scheduled visits with the treating physician for PD (yes, no)
- Any extra or unscheduled visits with the treating physician for PD (yes, no)
- Been seen in the Emergency Room due to PD (yes, no)
- Hospitalization (yes, no)
  - If yes: due to PD (yes, no)
- Overall treatment preference from physician's profile (LCIG as monotherapy, LCIG plus add-on PD medication)

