#### 7.8 Regression analyses

For the application of regression analysis, missing/unknown data for prognostic factors are imputed. Imputation is planned to be accomplished by a regression based single imputation method where missing values of one predictor variable are predicted by regression models with a set of remaining potential prognostic variables as independent variables. This might require adequate preprocessing of the data. Modification of this imputation strategy is possible if implied by the data.

Regression analyses will be evaluated for FAS and conducted on imputed data.

Regression analyses will be performed separately for each of the two primary variables (see Section 6.4):

LCIG monotherapy 1 (LCIG monotherapy 2, respectively) at 12 months after LCIG initiation will be used as dependent (i.e. response) variable in two multivariable logistic regression models. The independent variables (i.e. potential predictors) will be checked for collinearity.

For the first multivariable logistic regression model the following variables will be considered as potential predictors (i.e. independent variables):

Table 7-2: Potential predictors used for regression analysis 1

Variable	Range	Dichotomization/Grouping
Age	numeric	-
Gender	Male, Female	Male vs. Female
Race	White, Black, Asian, Mixed, Other	White vs. Non-White
Education	No formal education, primary school, secondary school, non-university professional education, university	Less than secondary school vs. secondary school or higher
Total number of symptoms	numeric	
Number of symptoms related to treatment	numeric	
Number of motor symptoms	numeric	-
Number of non-motor symptoms	numeric	-
Total daily LEDD at LCIG initiation	numeric	-
Time from PD diagnosis to start of LCIG	numeric	-
Duration of 'Off' state time during a 24h period	numeric	-
Duration of dyskinesia during a 24h period	numeric	-
UPDRS V prior to LCIG initiation (if available)	numeric	-
Any device aided therapy other than LCIG in the past	Yes, No	Yes vs. No
Any dopamine agonists in the past	Yes, No	Yes vs. No
PD motor phenotype	Tremoric, Akinetic rigid, Mix	
Time from PD diagnosis to motor fluctuation	numeric	
Time from PD diagnosis to onset of morning akinesia	numeric	
Country		
GNI	numeric	

Categorical predictors will be dichotomized / grouped as shown in Table 7-2 in order to simplify interpretation.

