Backward elimination with a significance level of 0.05 will be applied to stepwise automatically select relevant predictors. Effect estimates and p-values will be given for each (potential) predictor.

For the second multivariable logistic regression model the following variables will be considered as potential predictors (i.e. independent variables):

Table 7-3: Potential predictors used for regression analysis 2

Variable	Range	Dichotomization/Grouping
Approximate number of APD patients treated per year	numeric	-
Years of LCIG experience	numeric	-
Years of DBS experience	numeric	-
Approximate number of APD patients treated with LCIG per year	numeric	-
Number of years physician has been working at the institution	numeric	-
Average number of PD and APD patients per year at center	numeric	-
Number of specialist physicians working with PD patients at center	Numeric	-
Origin of service at center	National health services, Private health services	National health services vs. Private health services
Average frequency of routine visits for APD patients on device aided therapy at center	< 1x/year, 1x/year, 2x/year, 3x/year, > 3x/year	≤ 1x/year vs. ≥ 2x/year
Country		
GNI	numeric	

Categorical predictors will be dichotomized / grouped as shown in Table 7-3 in order to simplify interpretation.

Backward elimination with a significance level of 0.05 will be applied to stepwise automatically select relevant predictors. Effect estimates and p-values will be given for each (potential) predictor.

For both regression models the Gross National Income (GNI) is defined as follows (source: https://data.worldbank.org/indicator/NY.GNP.PCAP.CD):

Country	GNI
Austria	45.44
Bulgaria	7.76
Canada	42.87
Czech Republic	18.16
Croatia	12.43
Estonia	18.19

Greece	18.09
Hungary	12.87
Ireland	55.29
Israel	37.27
Netherlands	46.18
Romania	9.97
Spain	27.18
Sweden	52.59

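### SAP 7.8, model 2: physician and centre factors are tested as if patients were independent, so null factors are kept too often if site or physician correlation remains after the country terms

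*SAP*

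**What the plan says.** SAP 7.8 takes LCIG monotherapy at 12 months (each of the two definitions in SAP 6.4) and states that it "will be used as dependent (i.e. response) variable in two multivariable logistic regression models". The first model holds mainly patient characteristics. The second (Table 7-3) has 11 candidates:

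- five that describe the physician: APD patients per year, LCIG patients per year, years of LCIG experience, years of DBS experience, years at the institution;
- four that describe the centre: patient volume, number of specialists, origin of service, visit frequency;
- Country and GNI.

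Selection is automatic: "Backward elimination with a significance level of 0.05 will be applied to stepwise automatically select relevant predictors". Reporting is complete: "Effect estimates and p-values will be given for each (potential) predictor".

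Patients are nested by design. SAP 4.2.1 requires that "Patients must be treated by the same physician (PI or co-investigator) since the initiation of LCIG treatment", and SAP 4.2 states that "All eligible patients at a given site were to be enrolled consecutively in order to minimize selection bias".

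Neither document names a random effect, GEE, a cluster-robust variance, an overdispersion correction or a site-level analysis. Protocol 9.9 says country would be considered when predictors are analysed; the SAP does this by listing Country as a candidate that elimination may drop.

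**The concern.** Each of the nine physician and centre factors takes one value for all patients of a physician or a centre. The information about such a factor comes mainly from the number of physicians or sites. Ordinary logistic regression counts some 400 independent patients instead.

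Correlation within sites is plausible because the outcome is itself a prescribing decision. The protocol's rationale reports differing approaches to add-on medication in routine practice. The physician's treatment preference and use of treatment algorithms are recorded but are not in Table 7-3, so any effect they have stays unmodelled at the level where the tested factors vary.

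At stake is a stated secondary objective: "To identify predictors for achieving long-term monotherapy with LCIG vs. LCIG plus add-on PD medication, based on the patient's profile and the physician's profile". Model 2 is the only regression on physician and centre characteristics. Chance variation between sites within a country could be reported as an effect of experience or volume.

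**Working it through.** **Plan's own figures.** None is given for the regressions. The only design figure is the 385 evaluable patients in protocol 9.5: 1.96² × 0.25 / 0.05² = 384.15, rounded up to 385. It is reproduced, but it concerns the primary percentages.

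**Inputs.** From the documents: about 400 patients (SAP 4.2), 14 countries (GNI table in SAP 7.8), nine physician or centre factors, elimination at 0.05. Assumed: outcome rate 50%, number and size of sites, physicians per site, ICC.

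**Step 1: one null factor, formula.** For a factor constant within sites of size m, the design effect is DEFF = 1 + (m − 1) × ICC. The true size of a nominal 5% test is 2 × [1 − Φ(1.96/√DEFF)].

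| Layout | ICC 0.02 | 0.05 | 0.10 | 0.20 |
|---|---|---|---|---|
| 50 sites × 8 | 0.066 | 0.092 | 0.133 | 0.206 |
| 80 sites × 5 | 0.059 | 0.074 | 0.098 | 0.144 |
| 200 sites × 2 | 0.052 | 0.056 | 0.062 | 0.074 |

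Example, 50 × 8 at ICC 0.05: DEFF = 1 + 7 × 0.05 = 1.35; 1.96/√1.35 = 1.69; size 0.092.

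A physician-level factor suffers less when a site has several physicians. In 50 sites × 2 physicians × 4 patients with site-level correlation, simulated size at ICC 0.05 / 0.10 was 0.068 / 0.084 for a physician-level factor and 0.086 / 0.131 for a centre-level factor.

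**Step 2: what country terms do.** Simulated size of one null site-level factor, 50 × 8, country dummies in the model, ICC 0.02 / 0.05 / 0.10 / 0.20:

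- all correlation between sites: 0.073 / 0.101 / 0.137 / 0.221;
- half between sites, half between countries: 0.064 / 0.070 / 0.103 / 0.155;
- all between countries: 0.056 / 0.052 / 0.048 / 0.053.

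Country terms remove the problem only to the extent that the correlation lies between countries.

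**Step 3: the SAP's selection rule.** Nine independent null factors, Country as a removable 13-df term, backward elimination at 0.05; GNI omitted because it is a fixed function of Country. Mean number of null factors kept, 50 sites × 8 (ranges are over repeated simulations of 500 to 2000 runs per cell):

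| Layout and correlation | ICC 0 | 0.02 | 0.05 | 0.10 | 0.20 |
|---|---|---|---|---|---|
| All nine vary by site; site-level | 0.44-0.49 | 0.58-0.63 | 0.78-0.87 | 1.36-1.39 | 2.15-2.24 |
| Five by physician, four by centre, 2 physicians per site; site-level | 0.38-0.47 | 0.50-0.56 | 0.73-0.75 | 1.00-1.01 | 1.52-1.61 |
| Same; physician-level | 0.46-0.50 | 0.42-0.49 | 0.59-0.60 | 0.78-0.80 | 1.24-1.27 |

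Multiplicity alone gives 9 × 0.05 = 0.45. With all correlation between countries and nine site-level factors, the mean is 0.47-0.55. With 80 sites × 5, all nine site-level, it is 0.45 at ICC 0, then 0.56 / 0.68 / 0.93 / 1.43.

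**Step 4: different assumptions.** A separate simulation used unequal sites, an outcome rate near 38% (the registry range in the protocol's background is 36-40%), added country differences and ICC on the logit scale. At ICC 0 / 0.05 / 0.10, retention per null factor was 0.065 / 0.115 / 0.160 with 40 sites and 0.062 / 0.098 / 0.129 with 60. Times nine, that is 0.59 / 1.04 / 1.44 and 0.56 / 0.88 / 1.16, the same picture.

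**Step 5: remedies.** A site random intercept (restricted pseudo-likelihood, t reference with between-site degrees of freedom), tested with Country held in the model, gave size 0.032-0.056 per factor. Used for selection under site-level correlation, it kept 0.37-0.57 null factors on average (50 × 8) and 0.38-0.50 (80 × 5); at least one was kept in 30-41% of runs. A plain sandwich variance had size 0.13-0.20 with 40 or 60 sites. A small-sample-corrected sandwich had size 0.020-0.033 with country dummies, which is conservative.

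**The case against.** The strongest reply is that the size is unknown. SAP 7.2 only promises to report the number of sites; physicians per site and ICC appear nowhere. At ICC 0.02 the single-test size stays between 0.05 and about 0.07, and with sites of two patients there is little inflation at any plausible ICC. Five of the nine factors belong to the physician, and SAP 4.2.1 allows a principal or a co-investigator, so treating all nine as site-level is an upper layout. All of this stands, and it is why the result is given as a range. Against it, unequal site sizes push the inflation up: with mean size 8, simulated size was 0.104 / 0.169 at ICC 0.05 / 0.10.

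Multiplicity is the larger problem at low ICC: with no clustering, about 35% of runs already keep at least one null factor. That stands too, and it is a separate fault that a clustering method does not cure.

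The study is exploratory: SAP 7.10 permits modifications and SAP 2.3 requires later changes to be described in the report. This lowers the severity but supplies no method, while SAP 2.5 says "The methods described in this SAP are mandatory for statistical programming". The collinearity check in SAP 7.8 concerns overlap among predictors, not correlated outcomes. It may reduce the number of candidates below nine.

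A reader might infer that leaving Country removable breaches protocol 9.9. It does not: that section says only that country would be taken into account, and both models offer it. That GNI is determined by Country is a separate matter, partly met by the collinearity check.

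**Conclusion.** The point holds as a conditional one. Followed as written, model 2 gives p-values that are too small for physician and centre factors whenever site or physician correlation remains after the country terms kept. Backward elimination then keeps null factors too often. The direction is secure; the size is not. For 50 sites of 8, the mean number of null factors kept rises from about 0.4-0.5 to about 0.6-0.9 at ICC 0.05 and 0.8-1.4 at ICC 0.10. The lower ends apply with two physicians per site, the upper ends when every factor varies by site.

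A reader might infer that the model 2 p-values are wrong in any event, or that about two false predictors should be expected. The documents support neither. With correlation wholly between countries and Country kept, or with very small clusters, the p-values are about right. The figure above two needs ICC 0.20 with all nine factors at site level. Nor does this point touch the primary percentages, which do not depend on model 2. It is worth correcting before analysis because the objective is stated and the remedy is cheap.

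**What to change.** In SAP 7.8, specify that model 2 is fitted with a random intercept for site, or for physician within site, and with between-cluster denominator degrees of freedom. Use the same model for every elimination step and for the reported p-values. Report the number of sites and physicians and the estimated site variance or ICC.

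If GEE is preferred, require a small-sample-corrected variance and state that it can be conservative with country terms; a plain sandwich is not adequate here. Keeping Country in throughout is optional. State in the report that multiplicity from backward elimination remains.

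The cost is a few lines of SAP text and standard SAS procedures, with elimination run step by step or by a short macro. No new data are needed. The price is wider intervals and fewer nominally significant predictors. If Country is held in, it uses about 13 degrees of freedom, and factors that differ mainly between countries will be estimated poorly.

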#### Parkinson's disease history

- Time since PD diagnosis calculated as year of visit minus year of PD diagnosis + 1
- Age at PD diagnosis calculated as year of PD diagnosis minus year of birth
- PD motor phenotype
- Time from PD diagnosis to motor fluctuation onset calculated as year of motor fluctuation onset minus year of PD diagnosis +1
- Time from PD diagnosis to start of LCIG calculated as year of first start date of LCIG initiation minus year of PD diagnosis +1
- Morning akinesia (yes, no)
  - If yes: time from PD diagnosis to onset of morning akinesia calculated as year of onset of morning akinesia minus year of PD diagnosis +1
- Wearing off (yes, no)
  - If yes: time from PD diagnosis to onset of wearing off calculated as year of onset of wearing off minus year of PD diagnosis +1
- Dyskinesia present (yes, no)
  - If yes: time from PD diagnosis to onset of dyskinesia calculated as minus year of onset of dyskinesia minus year of PD diagnosis +1

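### Onset time of morning akinesia is entered as a numeric predictor for the whole FAS, although it is undefined for patients without the symptom

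*SAP*

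**What the plan says.** SAP 6.3 (Parkinson's disease history) records a filter question, "Morning akinesia (yes, no"), and places the onset time beneath it: "If yes: time from PD diagnosis to onset of morning akinesia". The time to motor fluctuations in the same list carries no such condition: "Time from PD diagnosis to motor fluctuation onset calculated as year of motor fluctuation onset minus year of PD diagnosis +1".

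SAP 7.8, Table 7-2, lists "Time from PD diagnosis to onset of morning akinesia" as a numeric predictor with no grouping and no companion yes/no term. The same table does use yes/no terms for past device-aided therapy and past dopamine agonists.

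On gaps in the data, SAP 7.8 states that "missing/unknown data for prognostic factors are imputed". The method is single imputation: "missing values of one predictor variable are predicted by regression models with a set of remaining potential prognostic variables". The analysis population is then fixed: "Regression analyses will be evaluated for FAS and conducted on imputed data". SAP 6.7 refers only to missing items of rating scales. Preprocessing and changes to the imputation strategy are allowed in general terms, without reference to any variable.

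**The concern.** A patient who never had morning akinesia has no onset year. The value is not unobserved; it does not exist, so no imputation model can estimate it. Section 7.8 has one rule for all gaps in the predictors and does not set this case apart.

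Three things are at stake.

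- Patients without the symptom would be analysed as if it had begun in a predicted year, and the coefficient per year would have no meaning for them.
- Whether a patient has morning akinesia, the simpler question and one already answered in the data, is not a term of its own. A null result for onset time could be read as showing that morning akinesia does not matter, which this model cannot show.
- The onset year has no upper limit. SAP Table 4-1 records PD history both before LCIG and at the visit, so an onset after the month-12 outcome could enter as a predictor of it. Protocol 9.7 describes the disease predictors as characteristics at LCIG initiation.

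Identifying predictors of monotherapy is a stated secondary objective (Protocol 8.0, SAP 3.2).

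**Working it through.** **1. The passages side by side.** The definition in SAP 6.3 leaves the variable blank for every patient who answers no. Table 7-2 and the FAS rule in 7.8 require a value for every patient. Two readings are possible:

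- *Blank counts as missing or unknown.* Section 7.8 then fills it by regression, and patients without the symptom receive a predicted onset time.
- *Blank does not count as missing.* The value stays empty and the patient drops out of the multivariable model. That contradicts analysis in the FAS and leaves only patients with morning akinesia.

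Under either reading, presence versus absence is not estimated as a term.

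**2. The plan's own figure.** Protocol 9.5 asks for a 95% confidence interval of ±5 points at an underlying 50%: n = 1.959964² × 0.25 / 0.05² = 384.15, rounded up to 385. This is reproduced and not in dispute; it serves as the number of patients below.

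**3. How many patients.** The documents give no prevalence of morning akinesia. The number without the symptom is 385 × assumed share: 38.5 at 10%, 77 at 20%, 115.5 at 30%, 154 at 40%, 192.5 at 50%.

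**4. Illustration by simulation.** Every input except n = 385 is an assumption.

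- There were 1,000 runs per row. Time from diagnosis to LCIG was normal with mean 12 and SD 5 years (minimum 2). Onset time was 0.6 × that time plus normal error with SD 2.5 (minimum 1).
- The true odds ratio for having the symptom was 0.5, and onset time had no effect.
- *As planned:* onset time for patients without the symptom is predicted by linear regression on time from diagnosis to LCIG, followed by logistic regression on onset time and that time.
- *Alternative:* a yes/no term, onset time nested within yes (centred there, 0 otherwise), and the same covariate.

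| Share without symptom | Planned onset term, p<0.05 | Its estimated OR per year | Yes/no term, p<0.05 | Its estimated OR |
|---|---|---|---|---|
| 10% | 5.8% | 1.000 | 51.8% | 0.483 |
| 20% | 4.5% | 1.000 | 77.4% | 0.485 |
| 30% | 4.2% | 1.002 | 86.2% | 0.495 |
| 40% | 4.9% | 1.000 | 90.9% | 0.494 |
| 50% | 4.2% | 1.003 | 92.0% | 0.495 |

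The planned term rejects at about its nominal 5%, as it should for an irrelevant variable. The table therefore shows only that an imputed onset time carries no information about presence. It is not a power calculation for the planned model, which has many more covariates.

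**5. Is the onset-time slope distorted?** The roles were reversed: presence had no effect and the true odds ratio was 0.90 per year of onset among patients with the symptom. The planned term estimated 0.899 with 20% and with 40% lacking the symptom. No bias appears in that setting.

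**The case against.** The case on the other side has several fair parts.

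- *The plan leaves room.* Section 7.8 foresees preprocessing and changes to the imputation, and SAP 7.10 allows modifications of any analysis. A careful analyst could handle the variable properly within these clauses. That stands, and for this reason it would be too strong to infer that invented onset times are certain. But the clauses name neither the variable nor the not-applicable case, and they defer the choice until the data are seen. The default as written remains faulty.
- *Presence is not ignored.* Nocturnal/morning akinesia is one of ten named motor symptoms in SAP 6.3. It adds one unit to the motor count and one to the total count, both in Table 7-2. SAP 7.4 also tabulates patient data by month-12 monotherapy group. A reader might infer that the symptom is never examined; the documents do not support that. What is missing is a separate regression term. A count gives every symptom the same coefficient and cannot isolate this one.
- *The simulation builds in its answer.* It makes presence the cause and onset time irrelevant, with assumed odds ratios and prevalences. That is correct, so it serves as illustration only.

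Two further inferences are tempting but unsupported. One is that morning symptoms are what separates monotherapy 1 from monotherapy 2. SAP 6.4 allows add-on treatment under definition 2 only once the day's infusion has ended in the evening, so a morning dose before the infusion does not fit it. The other is that imputation biases the onset-time slope; step 5 found no bias when presence has no effect.

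**Conclusion.** The concern holds as a faulty specification of one predictor. The definition in SAP 6.3 and the use in SAP 7.8 cannot both be followed for a patient without morning akinesia, and the general flexibility clauses do not resolve this.

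Its size is unknown, because it depends on a prevalence that the documents do not give. If nearly all patients have the symptom, little changes; if a third or a half lack it, the reported coefficient rests in good part on predicted values.

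The reach is limited. The variable is one of 20 candidates in the patient-profile model, which is fitted once for each monotherapy definition; the physician and centre model of Table 7-3 does not contain it. The analysis is secondary and exploratory. A reader might infer that the monotherapy percentages are affected, but they do not use this variable. The plan should be corrected, as the data for it are already collected.

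**What to change.** 1. In Table 7-2, add a yes/no term for morning akinesia before LCIG initiation. Use the nocturnal/morning akinesia item that SAP 6.3 already records for the time immediately before LCIG start. This avoids rebuilding presence from the onset year, which cannot order two events within one calendar year. Treat an answer of unknown as truly missing.
2. Either drop onset time from the model and keep it as a descriptive variable among patients with the symptom, or keep it nested within yes: centred among patients with the symptom and set to 0 for all others. Count only onsets not later than the year of LCIG initiation.
3. In SAP 7.8, state that a value undefined because the symptom is absent is not imputed, and that onset time is imputed only where it is truly missing among patients with the symptom.

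The cost is some SAP wording and one derived variable from data in hand. If onset time is kept, the model has one extra term. The new item also covers nocturnal akinesia, so it is somewhat broader than the filter question in the PD history, and it is contained in the motor count; the collinearity check already planned in 7.8 should include it.
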